9.1.2 Short description of endpoints and time periods

The primary and all secondary endpoints are limited to the primary intervention period. The majority of the exploratory endpoints, in line with the exploratory objectives, are related to both the primary and long-term intervention periods.

9.2 Description of statistical analysis

The following sections describe the estimands for the primary and key secondary objectives / endpoints, the overall testing strategies and the overall analysis methods.

9.2.1 Estimands for primary and key secondary objectives

The main treatment policy estimands for the primary and key secondary objectives of this study, are defined in Table 9.2 below. This table describes the four attributes of target population, endpoint, strategy for addressing intercurrent events, and population-level summary for the endpoints (ICH E9 (R1)).

Target population	Endpoint	Strategy for addressing intercurrent events	Population-level summary				
Primary object	Primary objective in line with H0_1_Primary						
Idiopathic Parkinson'sChange baselinefrom to 		All available data to be included. This is in alignment with the FAS definition. If a patient has a fall up to week 12 and has available week 12 gait data, then the week 12 data will be used and the fall ignored. If the week 12 measurement is not available, whatever the reason (death or injury) the baseline data are used (the patient is not excluded).	In Idiopathic PD patients on CPt, what is the change in gait velocity 12 weeks after randomisation, assessed during the 6MWT, between Conventional Physiotherapy and FeetMe Rehabilitation and whilst the patient is on treatment?				
Key secondary	objective in line w	ith H0_2_KeySecondary					
Idiopathic Parkinson's Disease (PD) patients on Conventional Physiotherapy (CPt)	Change from baseline to Week 12 in stance time variability (ms) assessed during the 6MWT.	All available data to be included. This is in alignment with the FAS definition. If a patient has a fall up to week 12 and has available week 12 gait data, then the week 12 data will be used and the fall ignored. If the week 12 measurement is not available, whatever the reason (death or injury) the baseline data are used (the patient is not excluded).	In Idiopathic PD patients on CPt what is the change in stance time variability 12 weeks after randomisation, assessed during the 6MWT, between Conventional Physiotherapy and FeetMe Rehabilitation and whilst the patient is on treatment?				

Table 9.2 Treatment policy estimands for the primary and key secondary objectives

9.2.2 Overall testing strategy

In line with the primary and key secondary objectives of the statistical analysis (see Table 9.2), a confirmatory hierarchical testing procedure will be applied. As a first step, the null hypothesis 'H0_1_Primary' will be tested at the 2-sided alpha level of 0.05. If this null hypothesis is rejected, the key secondary endpoint hypothesis 'H0_2_KeySecondary' will then be tested in a second step, again using a 2-sided alpha of 0.05.

H0_1 Primary: The null hypothesis to be tested for the primary endpoint is that the change in week 12 gait velocity from baseline in FeetMe Rehabilitation arm is equal to that in the conventional physiotherapy arm. The alternative is that they are not equal. Superiority will be declared if the difference (FeetMe Rehabilitation vs Conventional Physiotherapy) is significantly greater than 0 at the two-sided type I error level alpha=0.05.

H0_2 KeySecondary: The null hypothesis to be tested for the key secondary endpoint is that the change in week 12 stance time variability from baseline in FeetMe Rehabilitation arm is equal to that in the conventional physiotherapy arm. The alternative is that they are not equal. Superiority will be declared if the difference (FeetMe Rehabilitation vs Conventional Physiotherapy) is significantly greater than 0 at the two-sided type I error level alpha=0.05.

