5.1 Appropriateness of Measurements

Several studies support the clinical utility of using gait parameters to provide insight into the efficacy of rehabilitation. Gait velocity appears as an outcome measure for therapies such as the LSVT BIG (Millage et al, 2016) or DBS (Roger et al, 2016) and for almost all alternative forms of physical exercises aiming at improving mobility of PD patients. In the European Physiotherapy Guideline for Parkinson's Disease walking speed is graded as a "critical outcome", with an importance score of 8.6 over 10 (Keus et al, 2014). The FeetMe devices provide the opportunity to objectively and reliably measure this important outcome.

During a discussion between the HAS and the Sponsor in February 2021, the agency has supported the proposal of using gait velocity as a primary endpoint for this study. The reason being that gait velocity is shown to correlate with several other aspects of disease, e.g. risk of falls or quality of life.

In one study conducted on individuals aged 70 and older, each 10 cm/s decrease in gait speed was associated with a 7% increased risk for falls (Verghese et al., 2009). Participants with slow gait speed (\leq 70 cm/s) had a 1.5-fold increased risk for falls compared with those with normal speed. Since these falls occur during walking, apart from reduced speed, gait disturbances such as changes in stride time variability, or medio-lateral symmetry are also associated with falls. Therefore, walking speed can be an optimal proxy measure for evaluating fall risk in PD patients (Creaby and Cole, 2018; Paul et al., 2013; Rodríguez-Molinero et al., 2019; Verghese et al., 2009).

For better interpretability of the change in velocity the key secondary outcome measure of stance time variability is introduced. This parameter is described to be related to balance and motor control (Rennie et al, 2020). It is expected that a quantitative change in the gait (i.e.: speed) complemented with the quality of the change (i.e.: stance time variability) will reflect the stability of the walk and will best depict the impact of the rehabilitation therapy.

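### The success rule for the key secondary endpoint has the wrong sign: a significant advantage for FeetMe in stance time variability cannot be declared superior, and a significant disadvantage would be

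*Protocol*

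**What the plan says.** Section 9.2.2 sets a two-step confirmatory hierarchy. H0_1 concerns gait velocity. If it is rejected, the key secondary hypothesis "will then be tested in a second step, again using a 2-sided alpha of 0.05".

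The H0_2 paragraph begins "The null hypothesis to be tested for the key secondary endpoint is that the change in week 12 stance time variability from baseline" and sets that change equal in the two arms. It continues "The alternative is that they are not equal", and ends with the same sentence that closes the H0_1 paragraph: "Superiority will be declared if the difference (FeetMe Rehabilitation vs Conventional Physiotherapy) is significantly greater than 0", at a two-sided level of 0.05.

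Table 9.2 in section 9.2.1 gives the key secondary endpoint as the change from "baseline to Week 12 in stance time variability (ms) assessed during the 6MWT". This is the raw variability, with no reversal of scale.

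Section 5.1 explains why the endpoint was chosen. It relates the parameter to balance and motor control and says that the quality of the change in gait ("i.e.: stance time variability) will reflect the stability of the walk"). Of gait variability more generally, it says that "gait disturbances such as changes in stride time variability, or medio-lateral symmetry are also associated with falls".

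**The concern.** Superiority is tied to a positive difference for two endpoints whose favourable directions are opposite. Faster walking is better, so a positive difference in the change in velocity favours FeetMe. More spread in stance time, in ms, means less regular gait, so a positive difference in the change in variability favours conventional physiotherapy.

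H0_2 is the second and last confirmatory step, so this sentence governs the only formal claim beyond the primary endpoint. Followed literally, it withholds the claim when FeetMe is significantly better and grants it when FeetMe is significantly worse. If the sign were reversed only after the results were known, the change would look post hoc, however innocent the original slip.

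**Working it through.** **1. The two rules side by side**

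| | H0_1 | H0_2 |
|---|---|---|
| Endpoint | Change in gait velocity (cm/s) | Change in stance time variability (ms) |
| Better direction | Higher (section 9.4 aims to improve speed) | Lower (inferred from section 5.1 and the ms scale) |
| Sign of FeetMe minus conventional physiotherapy if FeetMe is better | Positive | Negative |
| Written condition for superiority | Greater than 0 | Greater than 0 |
| Consistent? | Yes | No |

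**2. Is the sign reversed anywhere else?** No section defines change as baseline minus Week 12, takes the arms in the opposite order for this endpoint, or calls a positive difference favourable. Sections 9.2.4 and 9.5.2 only refer back to the primary method. A hidden convention would have to apply to H0_2 and not to H0_1, although both use the same wording.

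**3. The plan's own sample size.** Inputs from section 9.4: difference 14 cm/s, SD of change 27 cm/s, two-sided alpha 0.05, power 80%.

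- SD of change with correlation 0.5: 27 × √(2 × (1 − 0.5)) = 27, as stated.
- Normal approximation: n = 2 × (1.960 + 0.842)² × (27/14)² ≈ 58.4, so 59 per group.
- Noncentral t: power is 0.798 at 59 per group and 0.804 at 60, so 60 per group, as stated.
- Dropout of 20%: 60 / 0.80 = 75 per group, as stated.

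The sample size reproduces and is not in question.

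**4. Probability that superiority is declared on H0_2, once that test is reached.** The protocol gives no effect size, SD or power for stance time variability. I therefore assume a range of true standardised differences d (FeetMe minus conventional physiotherapy, negative meaning benefit) with n = 60 evaluable per arm. The largest value, 14/27 = 0.519, is borrowed from the primary endpoint for scale only. A two-sample t test stands in for the cLDA model.

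- Degrees of freedom: 2 × 60 − 2 = 118; critical value t(0.975) ≈ 1.98.
- Noncentrality: d × √(60/2) = d × 5.477. For d = −0.519 this is −2.84.
- Rule as written: P(T > 1.98). Corrected rule: P(T < −1.98).

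| True d | Rule as written (> 0) | Corrected rule (< 0) |
|---|---|---|
| −0.519 (benefit) | 0.0000009 | 0.804 |
| −0.3 | 0.0002 | 0.371 |
| −0.2 | 0.0012 | 0.191 |
| 0 | 0.025 | 0.025 |
| +0.2 (worsening) | 0.191 | 0.0012 |
| +0.3 | 0.371 | 0.0002 |
| +0.519 | 0.804 | 0.0000009 |

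The small probabilities under benefit are chance results in the wrong direction. They do not mean that the rule sometimes recognises a benefit.

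**5. Effect of the gate.** H0_2 is tested only after H0_1 is rejected, so the unconditional probability of a key secondary claim is lower. If both tests had power 0.804, the joint probability with the corrected sign would be 0.804² ≈ 0.65 under independence. It would lie between 2 × 0.804 − 1 ≈ 0.61 and 0.80 depending on the correlation.

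**The case against.** The best counter-argument is that the protocol never says in words that lower stance time variability is better. The remark about falls concerns stride time rather than stance time, and speaks of changes rather than increases. The favourable direction is therefore inferred. This is true, but the inference is hard to avoid: a spread in ms, offered as a measure of stability, has no plausible reading in which more is better. That the direction is left unstated is part of the defect, and the fix should supply it.

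A second argument is that this is plainly a copied sentence. The null, the two-sided alternative, alpha and the model are sound, and the estimate with its confidence interval would show the true direction whatever the label. This stands as a limit on the consequence: the data and the test are unharmed, and only the declaration is wrong. But the declaration is what a confirmatory rule exists to fix in advance. Section 9 gives the analysis to a blinded independent statistician, who should be able to apply the rule as written. Leaving detail to the SAP does not help either, because a SAP that used the opposite sign would contradict the protocol.

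A third argument is that the probabilities rest on a borrowed effect size and ignore the gate. That is fair, and it is why a range and the gated figures are given. The defect is one of logic and does not depend on any of these numbers.

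**Conclusion.** The concern holds. As written, H0_2 can declare FeetMe superior only when stance time variability rises significantly more, or falls significantly less, on FeetMe than on conventional physiotherapy. A significant advantage for FeetMe can never meet it. At an assumed benefit of 0.519 SD with 60 per arm, the H0_2 test declares superiority with probability of about one in a million instead of 0.804; a worsening of the same size is declared superior with probability 0.804.

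The conclusion rests on one inference, that lower variability is favourable. The probabilities rest on the assumed effect sizes and on a t test in place of the cLDA model. The primary rule, the type I error level, the hierarchy and the planned 150 patients are unaffected. Because this is a confirmatory decision rule, it must be corrected before any results are seen.

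**What to change.** In the H0_2 paragraph of section 9.2.2, make two changes:

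1. State that a decrease in stance time variability is favourable, and that change is Week 12 minus baseline.
2. State that superiority of FeetMe is declared if the difference in change (FeetMe minus conventional physiotherapy) is significantly less than 0 at two-sided alpha 0.05.

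Keep the greater-than-0 rule for gait velocity only, and use the same H0_2 rule in the SAP.

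As a precaution, state the favourable direction for swing asymmetry, MDS-UPDRS Part III and PDQ-39 as well. The protocol attaches no superiority rule to these, so there is no inequality to correct.

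The cost is a sentence or two in the protocol and the matching text in the SAP. Nothing changes in data collection, model, alpha, hierarchy or sample size.

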9.2.3 Analysis of the primary efficacy outcome

The primary analysis of the primary endpoint will be performed in line with the primary objective and the treatment policy estimand as outlined in Table 9.2. We will use the constrained longitudinal data analysis (cLDA) model which allows to analyse all available data.

As secondary analysis of the primary end point a sensitivity analysis will be performed excluding patients from the FAS population who have a change in levodopa medication during the first 3 months.

All basic data will be described.

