8.2 Medical History

A complete past medical history will be collected by the Investigator or appropriate site staff according to standard practice and recorded in the eCRF. This will include a history of all previous diseases and illnesses, those currently being treated until the time of the screening visit, as well as those which have any residual effects on the patient's health. Moreover, surgical history will be collected, including all invasive procedures the patient has undergone until the time of the screening visit. Previous falls should be recorded to the extent possible.

8.3 **Prior- and Concomitant Medication**

Details of all medication taken \leq 3 months prior to the Screening Visit or during the study until the EOS Visit will be collected by the Investigator or the site staff according to standard practice and recorded in the eCRF.

Patients are eligible if on stable treatment of PD medication for at least 30 days before screening. Major changes in PD treatment during the first 3 months of the study are not allowed. What is considered a major change is up to investigator judgement, nevertheless, in principle anything that would alter the gait of the patient is considered as such. For example, adaptation of the levodopa dose to maintain current level of ambulation is not considered a major change, while changing the posology of the

treatment (e.g.: switching from per os to parenteral), or introducing a new one would classify as one. Ideally no major changes should be issued during the whole duration of the study in other medication that can influence overall data interpretation either (e.g.: antidepressants).

In case major changes in concomitant medication are unuvoidable, either due to the worsening of a disease or a new disorder, it must be recorded in the eCRF specifying the reason (e.g.: worsening of a medical history, adverse event or as a new adverse event) and will be taken into account during analysis.

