9.5.1 Analysis for the primary endpoint

The primary outcome (the change in the gait velocity between baseline and week 12, assessed during the 6 Minutes Walk-Test) will be estimated and compared between Feetme rehabilitation and conventional physiotherapy groups using the constrained longitudinal data analysis (cLDA) model proposed by Liang and Zeger including centre as random effect and adjusted for the covariable "already in a rehabilitation program" considered as stratification factor in the randomisation. We chose to use cLDA model in view of its potential advantages compared to the conventional ANCOVA model. First, the cLDA model provides more flexibility in handling missing data by including all observed data, which, in general, results in more power when testing treatment differences compared with the longitudinal ANCOVA model. Second, compared with the ANCOVA model, the cLDA model provides more appropriate confidence interval estimates, especially in the context of randomised clinical trials where proper randomisation ensures baseline balance. In the cLDA model, both the baseline and postbaseline values are modelled as dependent variables using a linear mixed model (using an unstructured covariance pattern model), and the true baseline means are constrained to be the same for the 2 treatment groups. The between-group mean differences in 12-week change in gait velocity will be estimated by the time-by-arm interaction as treatment effect size. The assumptions of the cLDA model will be checked. We will use the analysis of cDLA model residuals by examining graphically the normality of residuals (histogram and Quantile-quantile plot) and by using the Shapiro Wilk test. In case of strong departure from the normality assumptions (even after applying a logarithmic transformation), nonparametric analysis will be used as recommended by Vickers et al. (reference: 1) Andrew J Vickers. Parametric versus non-parametric statistics in the analysis of randomised trials with non-normally distributed data. BMC Medical Research Methodology 2005, 5:35 2) Conover WJ, Iman RL: Analysis of covariance using the rank transformation. Biometrics 1982, 38:715-724.); absolute changes between baseline and 12-week will be calculated and compared between the 2 treatments groups using nonparametric analysis of covariance adjusted for baseline values. The effect size will be assessed by Hedges's g (standardized differences) computed on rank transformed data with its 95% confidence interval (using the method based on noncentral Student distribution which is a corrected version of Cohen's d taking into account the sample size). A sensitivity analysis will be performed excluding from the FAS population patients who have a change in levodopa medication during the first 3 months. For this sensitivity analysis, we will use the same methodology as that described for the primary analysis.

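### The levodopa sensitivity analysis tests medication confounding only incompletely: its exclusion rule does not match the protocol's own definition of a major change in PD treatment

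*Protocol*

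**What the plan says.** **The rule on medication (Protocol 8.3).** The restriction covers PD treatment as a whole: "Major changes in PD treatment during the first 3 months of the study are not allowed". What counts as major is left to the investigator, with the guide that "in principle anything that would alter the gait of the patient is considered as such". Two examples mark the boundary. On the permitted side, "adaptation of the levodopa dose to maintain current level of ambulation is not considered a major change". On the other side stand a change of posology, illustrated by a switch from oral to parenteral, "or introducing a new one would classify as one". If a major change in concomitant medication cannot be avoided, it is recorded in the eCRF with its reason and "will be taken into account during analysis".

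**The analysis (Protocol 9.2.3 and 9.5.1).** The secondary analysis of the primary endpoint in 9.2.3 is done "excluding patients from the FAS population who have a change in levodopa medication during the first 3 months". Section 9.5.1 repeats it: "A sensitivity analysis will be performed excluding from the FAS population patients who have a change in levodopa medication during the first 3 months", with the same method as the primary analysis. Neither section refers to 8.3, limits the exclusion to major changes, or names any PD drug other than levodopa. Section 9.1 defines no per-protocol set.

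**The concern.** The protocol uses two different criteria for the same issue. Section 8.3 sorts medication changes by whether they alter gait, across all PD drugs. Sections 9.2.3 and 9.5.1 sort them by whether the drug is levodopa, whatever the effect on gait. The two groupings overlap only in part.

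Gait velocity is the primary endpoint, so a PD drug change that alters gait is an obvious competing explanation for a difference between arms. The trial is open label and the investigator judges what is major, so such changes could differ by arm. A reader of the report would take the sensitivity analysis as evidence that medication did not drive the result. It could give that reassurance while patients whose gait was altered by a new non-levodopa drug are still in it. This is not a detail left to the SAP: the protocol fixes the criterion twice. An SAP that copies 9.2.3 would have no check that covers other PD drugs, unless it adds one.

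**Working it through.** **Step 1. Put the two rules side by side.**

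| Change in the first 3 months | Status under 8.3 | Treatment under 9.2.3 / 9.5.1 |
|---|---|---|
| Levodopa adapted to maintain ambulation | Not major | Excluded |
| Major change to levodopa (e.g. route) | Major | Excluded |
| New non-levodopa PD drug, levodopa unchanged | Major | Kept |
| Other gait-altering change to a non-levodopa PD drug, levodopa unchanged | Major | Kept |

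The rules agree on the second row only.

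**Step 2. Confirm that the design figures are not touched.** Inputs from 9.4: difference 14 cm/s, SD of the change 27 cm/s, correlation 0.5, two-sided alpha 0.05, power 80%, dropout 20%.
- SD of the change: 27 × √(2 × (1 − 0.5)) = 27 cm/s, as stated.
- Two-sample t-test: 59.4, rounded up to 60 per group, as stated.
- Dropout: 60 / (1 − 0.20) = 75 per group, 150 in total, as stated.

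None of these depends on the sensitivity analysis.

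**Step 3. What the current rule costs in patients (illustrative).** The protocol gives no frequency of levodopa changes, so the share q is assumed and taken as equal in both arms. Evaluable n per arm = 60 × (1 − q); t-test power for 14 cm/s with SD 27:

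| q | n per arm | Power |
|---|---|---|
| 0% | 60 | 80% |
| 5% | 57 | 78% |
| 10% | 54 | 76% |
| 20% | 48 | 71% |
| 30% | 42 | 65% |

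Power is only a rough yardstick for an analysis outside the confirmatory hierarchy. The table shows how much precision goes on removing patients, some of whom 8.3 does not regard as having a major change.

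**Step 4. What the current rule leaves in (illustrative).** Suppose a fraction m of one arm, in excess of the other, has a retained non-levodopa major change that shifts week-12 velocity by s. The arm difference then keeps m × s. Both ranges are assumptions; for s the small and large values quoted in 9.4 are borrowed (6 and 22 cm/s).
- Low end: 0.05 × 6 = 0.3 cm/s.
- Middle: 0.10 × 14 = 1.4 cm/s.
- High end: 0.20 × 22 = 4.4 cm/s.

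Against 14 cm/s these are 0.3/14 = 2%, 1.4/14 = 10% and 4.4/14 = 31%.

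**Step 5. Would keeping the patients and blanking their week-12 value be better than excluding them?** In the primary period the in-clinic 6MWT is done at baseline and Visit 3 only (Table 6.1, 8.1.1). Blanking the week-12 value therefore leaves a baseline-only patient. With two time points, a common baseline mean and unstructured covariance, the likelihood splits into a part for baseline and a part for week 12 given baseline and arm. The arm difference sits entirely in the second part, to which a baseline-only patient contributes nothing. Five simulated trials (60 per arm, 10% blanked in one arm and 30% in the other) confirmed it: both approaches gave the same estimate to within numerical tolerance, for example 12.591 and 12.591 cm/s. A random centre effect and the stratification covariate break the exact identity, but there is no reason to expect a material gain.

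**The case against.** **The purpose of the analysis is not stated.** Sections 9.2.3 and 9.5.1 do not say what the check is for, so tying it to 8.3 is an inference. This stands. A reader might infer that the analysis fails altogether to test what it was meant to test. The documents do not support that: no purpose is given, and the rule does remove every major change to levodopa.

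**Dropping permitted adaptations is defensible.** A dose adapted to hold ambulation steady can mask worsening gait, so a result free of any levodopa change answers a legitimate question. Because major changes are prohibited, adaptations may also be the more common event. This stands too, and is the reason to keep the analysis. It does not close the gap for other PD drugs.

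**The commitment in 8.3 names no method, and the SAP may honour it.** This is correct as far as it goes. A reader might infer that the commitment is already broken, and that cannot be shown from the protocol alone. What can be shown is that the one criterion the protocol fixes does not cover the changes that 8.3 describes.

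**An 8.3-based trigger is softer.** Whether levodopa changed is a fact; whether a change is major is an investigator's judgement in an open-label trial. This is a fair point, and the fix has to deal with it.

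**Excluding on a post-randomisation event loses the protection of randomisation.** True, but equally true of either definition. It is a reason to read both analyses as supportive, not an argument for one over the other.

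**Conclusion.** The point holds as a mismatch between two fixed passages. The only medication-related check of the primary result removes patients whose change 8.3 treats as permitted and keeps patients whose change 8.3 treats as gait-altering when the drug is not levodopa. It tests medication confounding incompletely.

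Its reach is limited. The primary analysis follows a treatment policy estimand and uses all available data whatever the medication change (Table 9.2), so the primary test, the key secondary test and the sample size are unaffected. A reader might infer that the primary result is biased by this rule; it is not, because the rule governs a supportive analysis only.

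The size cannot be settled from the protocol. On the assumed ranges above, 0.3 to 4.4 cm/s could remain in the sensitivity result. The upper end needs 20% of one arm to have a large-effect change that is absent from the other arm, which is demanding when such changes are prohibited and patients expected to need one are ineligible. It should be corrected before the analysis is run, but it does not threaten the trial's main conclusion.

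**What to change.** 1. In 9.2.3 and 9.5.1, define the sensitivity analysis by a major change in PD treatment as described in 8.3, for any drug, during the first 3 months.
2. Classify changes from the eCRF record, without knowledge of arm and before database lock.
3. Keep the existing exclusion of patients with any levodopa change as a separate, labelled supportive analysis.
4. Report by arm the number of patients with each type of change: levodopa adaptation, major levodopa change, and major change in another PD treatment.
5. State that both analyses condition on a post-randomisation event and are supportive only.

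Replacing exclusion by setting the week-12 value to missing is not worth adopting. It gives essentially the same estimate, and the Table 9.2 rule that baseline data are used when week 12 is unavailable could then be read as imputing no change.

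**Cost.** One additional supportive analysis and a blinded classification of recorded changes. No new data collection is needed, since 8.3 already requires major changes and their reasons in the eCRF. The change concerns the analysis definition only; no rule on medication is proposed.
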